8.2 Bivariate interference

Both dependent variables, number of reintubations and time of weaning, are quantitative. The relation between number of reintubations and each protocol, will be contrasted using **T-Student test**. The relation between time of weaning and each protocol will be contrasted using **Kaplan-Meier**, as it is a survival analysis.

The relation between **quantitative covariates** and each protocol, will also be contrasted using **T-Student test**.

And the relation between **qualitative covariates** and each protocol will be contrasted by **Xi-squared test** or **Fisher's exact test** (if the expected number of cases in a cell will be less than 5).

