7.3 Sampling

7.3.1 Sample size

We estimated the sample size using the free online software GRANMO, and the setting for two independent proportions.

In the view of the literature published so far, the proportion of reintubation in preterm newborns that are on invasive mechanical ventilation is 16% (studies differ between 12% and 20%, an average has been made).(62,63)

Accepting an alpha risk of 0.05 and a beta risk of 0.2 in a two-sided test, **271** subjects are necessary in first group and **271** in the second to recognize as statistically significant a difference greater than or equal to 0.1 percent units. A proportion in one of both groups has been estimated to be 16%. It has been anticipated a drop-out rate of 5% (0,05).

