7.4 Variables and measurements

Independent variable

The independent variable is the **invasive mechanical ventilation protocol** used during the weaning. It is conceived as a **dichotomous qualitative nominal variable** and is expressed as PSV/ACVGV:

- PSV: Pressure support ventilation
- ACVGV: Assist control volume guarantee ventilation

Dependent variables

There are two dependent variables: **number of reintubations** and **time of weaning**.

The **number of reintubations** is the main dependent variable. It is a **discrete quantitative variable**. The higher the number of reintubations, the higher the risk of complications, so it is a good variable to determine which protocol is more effective. Extubation failure is defined as reintubation within 24-72 hours, so the number of reintubations will be counted for the first 72 hours after the extubation.

The **time of weaning** is the secondary dependent variable. It is a **continuous quantitative variable**. It is counted from the moment the weaning is started until the extubation is executed. The longer this time is, the greater the risk of complications arising from invasive ventilation that the child may have, so it is a good variable to determine which protocol is more effective.

Covariates

- **Gestational age at birth/type of preterm:** once is born, the baby will be classified into one of these categories. It is a *dichotomous qualitative ordinal variable*:
 - Extremely preterm (< 28 weeks of gestation)
 - Very preterm (28-32 weeks of gestation)
- **Birthweight:** it is a *continuous quantitative variable* measured in grams.
- **Sex:** it is a *dichotomous qualitative nominal variable*. Categorized as men or women.
- **CPR after birth:** it is a *dichotomous qualitative nominal variable*. It will be expressed as yes or no.

- **5-minute Apgar score** (see Annex 1): It is a quantitative variable, but categorized in the following intervals, resulting in a *polychotomous qualitative ordinal variable*:
 - Apgar 0-3
 - Apgar 4-6
 - Apgar 7-10
- **Risk factors of prematurity:**
 - **Previous preterm birth:** it is a *dichotomous qualitative nominal variable*. It will be expressed as yes or no.
 - **Second trimester miscarriage (> 16 weeks):** it is a *dichotomous qualitative nominal variable*. It will be expressed as yes or no.
 - **Multiple pregnancy:** it is a *dichotomous qualitative nominal variable*. It will be expressed as yes or no.

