8.1. Descriptive analysis

First, we will summarize all dependent, independent variables and covariates.

- **Qualitative variables** (protocol used, type of preterm, CRP after birth, 5-minute Apgar score and most covariates related with risk factors) will be described using **proportions**.
- **Quantitative variables** (number of reintubations, time of weaning, birthweight, maternal age, and maternal size) will be summarized by **means, standard deviation, medians, and interquartile range (IQR)**

The dependent variables are quantitative, so a comparison of medians will be made in relation to the assigned protocol, PSV or ACVGV, will be done. These descriptives will be stratified by the categories of the covariates.

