8.3 Multivariate interference

It will be necessary to do a multivariate analysis adjusting the covariates according to the independent variable with the dependent variables that can interfere in the results, to avoid possible confusion.

Poisson regression model will be used for the association between the intervention and the number of reintubations, which is a **discrete quantitative variable**.

Cox regression models will be used for the association of the intervention with the **time** of weaning, which is a **continuous quantitative variable**. It is calculated as a survival analysis.

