- 6. Formation sessions** (April 2024): An online meeting will be held with the whole team to provide theoretical training on neonatal resuscitation and neonatal mechanical ventilation. Particular emphasis will be placed on invasive mechanical ventilation and weaning. During this meeting, a consensual and detailed document will be sent to the hospital coordinators of each centre with the values of each parameter of the ventilator necessary for both the initiation of weaning and extubation. It will also include the clinical and gasometrical criteria for weaning, extubation and reintubation.

The aim of this training is to homogenise the process and reduce differences in the results between centres.

- 7. Creation of a database** (April 2024): A computer scientist will be hired to create a database, so that the data collected before, during and after the intervention can be correctly recorded.

STAGE 3: Sample recruitment, intervention, and data collection (27 months: May 2024 – July 2026)

8. Sample recruitment: As mentioned above, a consecutive stratified sampling method of extremely and very preterm newborns with NRDS that are on invasive mechanical ventilation, admitted to the NCIU of the participating hospitals will be carried out. Each co-investigator at each centre will be responsible for enrolling patients who meet all the inclusion criteria and any of the exclusion criteria, after the parents or legal guardians have signed the informed consent form (see Annex 5). Each participant will be randomised to one of the intervention groups of the clinical trial. The hospital coordinators of each centre will supervise this process.

Recruitment will continue until each centre has recruited the number of participants assigned by the stratification, with a 1:1 ratio. This is expected to take approximately 26 months (2 years and 2 months).

9. Intervention: During this period, patients will be assigned to one of the protocols for weaning, PSV in one arm of the study and ACVGV in the other.

This process can take a few days or even a few weeks, so an extra month has been added to the projected 26 months for this stage.

10. Follow up: After the intervention, all patients enrolled in the study will be followed for the first 72 hours after extubation, as all clinical data will be recorded in the baby's medical record.

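### Reintubation is sized as a proportion but modelled by Poisson regression with no stated variance correction, and no single analysis is named as primary

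*Combined protocol and SAP*

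**What the plan says.** **Sizing.** Section 7.3.1 uses "the setting for two independent proportions". It states that "the proportion of reintubation in preterm newborns that are on invasive mechanical ventilation is 16" per cent, averaged from studies between 12% and 20%. It continues: "Accepting an alpha risk of 0.05 and a beta risk of 0.2 in a two-sided test", with a difference of 0.1 and 5% drop-out, giving 271 per group.

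**Outcome.** Section 7.4 classes reintubation as a discrete quantitative variable and says that "the number of reintubations will be counted for the first 72 hours after the extubation". Section 7.7 has the researcher evaluate reintubation at 72 hours. The data form in Annex 7 has one field for reintubation and none for the number or times of events.

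**Analysis.** Three treatments of this outcome are planned:
- Section 8.1, descriptive: means, standard deviations, medians and IQR, and "a comparison of medians will be made in relation to the assigned protocol".
- Section 8.2, bivariate: "The relation between number of reintubations and each protocol, will be contrasted using" a Student t-test. Chi-squared and Fisher tests appear only for qualitative covariates.
- Section 8.3, multivariate: "Poisson regression model will be used for the association between the intervention and the number of reintubations", adjusted for covariates. No robust variance or dispersion term is mentioned.

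Section 8 applies p < 0.05 to all analyses. No section says which result decides the main hypothesis.

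**The concern.** A Poisson model takes the variance to equal the mean. For a yes/no outcome with probability p the variance is p(1 − p), which is smaller, so standard errors computed under the Poisson assumption are too large. If Section 8.3 is run with model-based standard errors, the main outcome gets confidence intervals that are too wide and the test falls short of the 80% power on which recruitment was based. Because neither the t-test nor the Poisson model is ranked first, the trial could also end with one significant and one non-significant answer to its main question and no rule for choosing between them.

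**Working it through.** **Step 1: reproduce the sample size.** Inputs from Section 7.3.1: 16%, difference 0.10, two-sided alpha 0.05, power 80%, drop-out 5%.

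n = (1.960 + 0.842)² × [0.16 × 0.84 + 0.26 × 0.74] / 0.10² = 7.849 × 0.3268 / 0.01 = 256.5, so 257 evaluable. 257 / 0.95 = 270.5, so 271. This matches the plan, so the stated difference has to be read as 10 percentage points. The alternative 16% versus 6% needs only about 158 to 162 per group.

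**Step 2: Poisson standard errors on a yes/no outcome.** For the log risk ratio with n = 257 per arm:
- Poisson: √[1/(n p₁) + 1/(n p₂)]
- Binomial (what a robust variance estimates): √[(1 − p₁)/(n p₁) + (1 − p₂)/(n p₂)]

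| Rates | Poisson SE | Binomial SE | Ratio |
|---|---|---|---|
| 12% both arms | 0.2547 | 0.2389 | 1.07 |
| 16% both arms | 0.2205 | 0.2021 | 1.09 |
| 20% both arms | 0.1973 | 0.1764 | 1.12 |
| 16% vs 26% | 0.1982 | 0.1775 | 1.12 |
| 16% vs 6% | 0.2986 | 0.2853 | 1.05 |

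With equal rates the ratio is 1/√(1 − p); at 16% it is 1/√0.84 = 1.09.

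**Step 3: error rates.** 200,000 simulated trials per row, 257 per arm, yes/no outcome, unadjusted tests; the figures are proportions of trials significant at 5%.

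| Rates | t-test | Chi-squared | Poisson, model-based | Poisson, robust |
|---|---|---|---|---|
| 16% vs 16% | 5.0% | 5.0% | 3.1% | 4.8% |
| 16% vs 26% | 80.1% | 80.1% | 71.9% | 79.3% |
| 16% vs 6% | 96.1% | 96.1% | 94.7% | 95.8% |

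The t-test and the chi-squared test gave the same decision in every trial. The t-test was significant and the Poisson model was not in 8.2% of trials at 16% versus 26%, and in 1.9% under no difference. The reverse never happened.

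**Step 4: medians.** An arm of 257 has a median above 0 only if at least 129 infants are reintubated. At 6%, 16% or 26% that probability is below 10⁻¹⁵.

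**Step 5: if repeat events occur.** Let a share q of reintubated infants have a second event; q is an assumption, as the documents give no figure. The variance-to-mean ratio is (1 + 3q)/(1 + q) − p(1 + q). At p = 0.16 and q = 0.10 it is 1.3/1.1 − 0.176 = 1.01, so the Poisson assumption is about right there. Simulated type I error of the Poisson model (20,000 trials each, 16% in both arms) is 3.8% at q = 5%, 5.0% at 10%, 6.5% at 20% and 7.6% at 30%.

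**The case against.** The best defence is that much of the plan works.

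- **The t-test is sound.** A reader might infer that all the planned tests have wrong error rates, or that the analysis never estimates what the trial was sized on. The documents do not support that. On a yes/no outcome the mean is the proportion, the difference in means is the risk difference, and the t-test has 5.0% type I error and 80.1% power. Its weakness is presentation and lack of rank.
- **The medians are descriptive.** Section 8.1 also reports means, and no decision rests on the medians.
- **Unadjusted then adjusted is a conventional sequence.** On a yes/no outcome, unadjusted, the Poisson model adds no false positives to the t-test. What is missing is a statement of which one counts.
- **A yes/no outcome is inferred.** Section 7.4 says number. A reader might take Section 10.3, "This process can take a few days or even a few weeks", as proof that a second reintubation cannot fall within 72 hours. That sentence describes the randomised weaning period and justifies one extra month; it says nothing about weaning again after a reintubation. The inference rests on the short window, the sizing, the follow-up wording and the single form field.
- **The variance estimator is unstated.** Section 8.3 does not exclude robust standard errors, and its model is covariate-adjusted, whereas the simulations are not.

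All of this stands, and it narrows the point. It does not remove the unspecified variance in Section 8.3 or the absence of a named primary analysis.

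**Conclusion.** The point holds in limited form and should be fixed. If the outcome is yes/no and Section 8.3 is run with model-based standard errors, they are about 9% too large at 16% (7% at 12%, 12% at 20%). Type I error is then about 3.1%, and power at the contrast that reproduces the sample size is about 72% instead of 80%. If the true contrast is 16% versus 6%, a reduction from 16%, the loss is only about one point (95% versus 96%).

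These figures assume no covariate adjustment and 257 evaluable infants per arm. It would be tempting to conclude that the Poisson error is always conservative. It is not established: above roughly 10% of reintubated infants with repeat events (an assumed share), it becomes anti-conservative. A reader might also infer that siblings from multiple pregnancies materially distort the result. Multiple pregnancy is recorded as a covariate, but the documents give neither the share of siblings nor their correlation, so no size can be put on this.

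**What to change.** 1. In Section 7.4, define the primary endpoint as any reintubation within 72 hours of the first extubation, yes or no. Keep the number of reintubations as a descriptive item; the form then needs a field for it.
2. In Section 8, name one primary analysis: a Poisson model with robust standard errors, or a log-binomial model, reporting the risk ratio and risk difference with 95% CI. State whether it is adjusted and for which covariates. At the planned sample size it has about 79% power for 16% versus 26%, and the robust variance does not rely on the Poisson variance assumption.
3. Label the t-test as supportive, and report proportions in place of medians for this outcome.
4. As a cheap addition, cluster the robust standard errors on the mother, which needs a sibling identifier on the data form.

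The cost is wording in Sections 7.4 and 8 and small changes to the data form. The sample size stays at 271 per group. The changes should be made before outcome data are seen, so that the choice of deciding analysis is credible.

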Annex 7 – Data form

ETIQUETA
IDENTIFICATIVA

DATA FORM

En relació amb el pacient

Setmanes de gestació	
Tipo de preterme	
Per al néixer	
Sexe	
CPR després de néixer	
Apgar score als 5 minuts	

En relació amb la mare

Part preterme previ	
Avortament del segon trimestre	
Edat	
Alçada	
Cirurgia cervical prèvia	
Anomalia uterina congènita	
Diabetis pregestacional	
Malaltia de transmissió sexual	
Fumadora	
Consum alcohol o altres tòxics	
Període intragestacional curt	
Infecció extrauterina	

En relació amb l'embaràs

Embaràs múltiple	
Corioamnionitis	
Ruptura prematura de membranes	
Diabetis gestacional	

En relació amb la intervenció

Codi del protocol utilitzat	
Reintubació	
Temps de weaning (en dies)

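### Siblings from multiple pregnancies can be enrolled, but no analysis allows for their correlation and the data form has no pregnancy code: a cheap gap to close, not a demonstrated error in the 5% level

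*Combined protocol and SAP*

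**What the plan says.** **Who can enter.** Section 7.2 defines eligibility for each neonate (born before 32 weeks, ventilated for NRDS, consent given) and does not restrict entry to singletons. Sampling is consecutive (7.3.2). Section 3.1.2 names multiple pregnancy as a risk factor for preterm birth, and section 7.4 and Table 4 list "Multiple pregnancy" as a yes/no covariate. The sponsor therefore expects such infants.

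**How they are allocated.** Section 7.3.4 describes electronic 1:1 randomisation of the patients within each hospital. Section 7.5 assigns each patient on meeting the weaning criteria. Section 10.3, Stage 3, says: "Each participant will be randomised to one of the intervention groups of the clinical trial". There is no rule for siblings and no statement about blocks.

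**How they are analysed.** For the main outcome, section 8.2 states "The relation between number of reintubations and each protocol, will be contrasted using" a Student t-test, and section 8.3 states "Poisson regression model will be used for the association between the intervention and the number of reintubations". Weaning time has Kaplan-Meier and Cox analyses. No random effect, GEE, frailty term or robust variance appears.

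**What is recorded.** Section 7.7 gives each infant a separate anonymous code. Annex 7 has a field "Embaràs múltiple" but no mother, pregnancy or birth-order field.

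**The concern.** Siblings share a mother, gestational age, antenatal exposures and usually the same unit, so their outcomes may be correlated. Adjusting for multiple pregnancy as yes/no moves a mean; it does not model the correlation between two infants of one pregnancy. An analysis that counts both as independent can state the wrong precision. How far, and in which direction, depends on whether siblings end up in the same arm or in different arms, and on whether the coefficient of interest is the treatment effect or a maternal characteristic. Without a pregnancy code the analyst cannot reliably see which infants belong together, and the code is far easier to collect prospectively than to reconstruct afterwards.

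**Working it through.** **1. The plan's own sample size.** Inputs from section 7.3.1: "Accepting an alpha risk of 0.05 and a beta risk of 0.2 in a two-sided test"; "A proportion in one of both groups has been estimated to be 16" percent; and a detectable difference read as 0.10 absolute ("to recognize as statistically significant a difference greater than or equal to 0.1 percent units"); dropout 5%. With 0.16 against 0.26 and the unpooled normal approximation:

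n = (1.960 + 0.842)² × (0.16×0.84 + 0.26×0.74) / 0.10² = 256.5, so 257 per arm; 257/0.95 = 270.5, so 271 per arm and 542 in total.

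This matches the stated figure, which therefore assumes independent infants with no design effect.

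**2. Variance of the treatment difference.** Let f be the share of infants whose sibling is also enrolled (pairs) and ρ the within-pair correlation. Relative to the independent-infant variance, the true variance is:

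- siblings always in the same arm: 1 + fρ
- siblings always in opposite arms: 1 − fρ
- each infant randomised independently: about 1, because a pair is equally likely to add +ρ or −ρ and the terms cancel on average.

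The documents give neither f nor ρ. Assumed ranges: f = 10% to 35%, ρ = 0.1 to 0.5, so fρ runs from 0.01 to 0.175.

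**3. Error rate of a nominal 5% two-sided test.** Error = 2 × [1 − Φ(1.96/√V)].

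| Allocation of siblings | V | True error |
|---|---|---|
| Same arm | 1.01 to 1.175 | 5.1% to 7.1% |
| Independent | about 1 | about 5% |
| Opposite arms | 0.99 to 0.825 | 4.9% to 3.1% |

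In the same-arm case, power = Φ(2.80/√V − 1.96) falls from 79.6% to 73.4%.

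**4. Simulation of the planned t-test under the null.** 20,000 trials of 514 infants, 16% event rate:

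| f, ρ | Same arm | Independent | Opposite arms |
|---|---|---|---|
| 0.2, 0.3 | 0.058 | 0.050 | 0.045 |
| 0.3, 0.5 | 0.066 | 0.051 | 0.033 |

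**5. The Poisson model.** Reintubations are counted for only 72 hours after extubation (7.4), and Annex 7 has a single reintubation field. If the outcome is nearly 0/1 at 16%, the true variance is p(1−p) while the model assumes p, a ratio of 1 − 0.16 = 0.84. Even the largest same-arm factor then gives 0.84 × 1.175 = 0.99. The figures in step 3 apply to a well-calibrated test such as the t-test and do not carry over to this model.

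**6. Mother-level covariates.** The 15 prematurity risk factors in section 7.4 describe the mother or the pregnancy and are largely the same for siblings. For a covariate constant within a pair, the factor is roughly 1 + fρ however the siblings are allocated, that is 1.01 to 1.175. Correct standard errors would be larger by a factor of √1.01 = 1.005 to √1.175 = 1.084. In the Poisson model the over-large variance in step 5 can offset this.

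**The case against.** The strongest reply is that, under the design as written, no error in the treatment comparison has been shown. Sections 7.3.4, 7.5 and 10.3 all describe randomisation of each patient, and in that case the t-test stays at about 5%. This stands, and it sets the limit of the point.

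A reader might infer more in four places, and the documents do not support it:

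- *That siblings will tend to be split by small permuted blocks.* Blocking is never mentioned. Infants are randomised when each meets the weaning criteria, so siblings need not be consecutive allocations.
- *That the upper figures are what to expect.* Each sibling must separately qualify. From section 7.3.3, only about 55% × 40% = 22% of these preterm infants have NRDS and are ventilated. Siblings probably resemble each other more than that implies, but if 60% of siblings were also enrolled, f = 35% would still need 0.35/0.60 = 58% of infants to come from multiple pregnancies.
- *That siblings can never be linked.* Gestational weeks, maternal age, height and obstetric history on Annex 7 might identify many sets. The matching is unplanned and open to error, but not impossible.
- *That triplets are foreseen.* The documents speak only of multiple pregnancy, and the arithmetic here is for pairs.

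The opposite-arm case is also conservative: it costs efficiency and does not breach the 5% level.

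What the reply does not remove: no allocation rule for siblings is stated, no analysis allows for the correlation, no pregnancy code is collected, and the mother-level coefficients are affected under any allocation. Section 12.1 relies on those adjusted models to judge confounding.

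**Conclusion.** The point holds as a worthwhile, inexpensive improvement. Multiples are eligible and expected, every planned analysis assumes independent infants, and the form does not link siblings. It would be tempting to conclude that the stated 5% level and the 95% intervals for the treatment effect are wrong. The documents do not support that, because individual randomisation keeps the unadjusted comparison at about 5%. Departures to 5.1%–7.1% (same arm) or 3.1%–4.9% (split) apply to the t-test only if siblings happen to fall that way, and they rest on the assumed ranges for f and ρ. Standard errors of mother-level covariates would tend to be too small, by up to about 8% on those assumptions, except where the Poisson variance is already too large.

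**What to change.** 1. Add a coded pregnancy identifier to Annex 7, shared by siblings and containing no personal data.
2. State in section 7.3.4 that siblings are randomised individually.
3. In section 8.3, use GEE or cluster-robust standard errors by pregnancy for the reintubation model, and a robust variance clustered on pregnancy for the Cox model. This gives valid intervals however siblings fall across the arms and also corrects the Poisson variance when the outcome is nearly 0/1. Take the treatment comparison on the main outcome from this model, or give its unadjusted form alongside the t-test.

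The cost is one form field, two or three sentences and slightly more analysis work. The sample size stays at 542. Inflation would arise only if siblings were deliberately kept in one arm, which the protocol does not propose. The field should be in place before recruitment starts.
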